However, infrequent but serious adverse events such as myopathy, neuropathy, and pancreatitis as well as renal impairment and reduced Bone Mineral Density (BMD) have been reported [Terrault, 2016]. NUCs-dependent nephrotoxicity was first observed in human immunodeficiency virus (HIV)-infected patients treated with adefovir (ADV) and primarily results in proximal tubular toxicity rather than glomerular toxicity, which was susceptible to the effects of mitochondrial toxicity [Fisher, 2001, Lampertico, 2016]. It was reported that proportion of patients with GFR-shifting from ≥ 90 to 60 - 89mL/min/1.73 m2 from baseline was 15%, 17.8% and 14.5% among LAM, ETV and TDF-treated non-cirrhotic compensated CHB patients respectively [Koklu, 2015]. However, HBV-infection, aging, comorbidity, e.g. hypertension, diabetes mellitus, is also linked to occurrence of chronic kidney disease in CHB patients besides NUC usage [Levey, 2012]. Hence, regular monitoring of renal function (including serum phosphate) as well as viral response is required in the management of CHB patients [Chinese Medical Association, 2015, Terrault, 2016, EASL, 2017]. Reduced BMD is another possible manifestation of renal toxicity due to renal proximal tubule damage leading to serum phosphate reduction and inadequate bone mineralisation [Kumar, 2012]. The

reported adverse effects of TDF on bone mineral density (BMD) are well known from its use in HIV treatment [Woodward, 2009].

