4. OBJECTIVES AND RESEARCH QUESTIONS

Study objectives and research questions are listed in the Table 2.

Table 2 Objectives and Research Questions

Objectives	Research Questions
Primary Objective To assess the effectiveness among overall and sub-group Chinese CHB patients who receive TDF treatment in real-world	Among the overall analysis population and relevant sub-group* populations: • Proportion of patients who achieve complete virologic response (CVR) at
	 weeks of 48, 96, and 144. Proportion of patients who achieve HBeAg loss and/or HBeAg. seroconversion in HBeAg positive patients at weeks of 48, 96 and 144.
	 Proportion of patients who achieve HBsAg loss and/or HBsAg seroconversion at weeks of 48, 96 and 144.
	 Proportion of patients who achieve transaminase normalization at weeks of 48, 96 and 144.
	 Time to CVR, defined as time from baseline to the first occurrence of CVR (if applicable)
Secondary Objective	
To assess the renal function change among overall and sub-group CHB patients during TDF	Among the overall analysis population and relevant sub-group* populations:
treatment	 Proportion of patients whose eGFR decline >20% from baseline at weeks of 48, 96,

Objectives	Research Questions
	and 144.
	 Percentage of change from baseline in eGFR at weeks of 48, 96, and 144
	Change from baseline in eGFR values at weeks of 48, 98 and 144
	 Proportion of patients with confirmed serum phosphate Grade 3 or 4 abnormality (<2.0 mg/dL) at weeks of 48, 98 and 144.
	 The percentage of change from baseline in serum phosphate at weeks of 48, 98 and 144.
	 Change from baseline in phosphorus values at weeks of 48, 98 and 144
Exploratory Objectives	
To explore the Bone Mineral Density (BMD) change among overall and sub-group CHB patients during TDF treatment	Percentage of BMD change from baseline at weeks of 48, 96, and 144
To investigate predictors of effectiveness among CHB patients who receive long-term	Baseline or on-treatment predictors (e.g. baseline characteristics, etc).
TDF treatment	Treatment effectiveness, including CVR, HBeAg loss and/or HBeAg, transaminage normalization
To explore risk factors of safety among CHB patients who receive long-term TDF treatment	Baseline or on-treatment risk factors (e.g. baseline characteristics, co-morbidities, and concomitant treatment etc).
	Renal impairment, including eGFR decline and serum phosphate
	Bone impairment, including BMD decline

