7.4. Adverse Events and Pregnancy Events Data Collection

As this study takes a naturalistic design and minimizes the level of interventions, only spontaneous AEs will be collected, i.e. all serious and non-serious adverse events (AEs) and pregnancy exposures related to any GSK product (e.g., Viread) will be collected and reported as described in the study-specific pharmacovigilance plan (sPVP). Our special interest is the renal and bone toxicity related to TDF. In routine clinical practice, collecting and reporting spontaneous AEs including pregnancy exposure is the obligation of physicians. Such events will be evaluated and reported by investigators completing the Spontaneous AE Reporting Form for HCPs, Pregnancy Initial Notification Form for HCPs and Pregnancy Outcome Form for HCPs. The study SAP will oversee the spontaneous AE reports to be forwarded by CRO to local safety team who will report to GSK central safety department.

See study Pharmacovigilance Plan (sPVP) for details. sPVP will include the following elements to ensure a comprehensive approach to safety event collection and reporting:

- Supplier pharmacovigilance training
- Investigator and site staff pharmacovigilance training
- Safety-specific roles
- AEs / SAEs and pregnancy exposures collection and reporting processes
- AEs / SAEs and pregnancy exposures collection forms
- Frequency of data review
- Reporting process and timelines

- Interim reports
- Study-specific PVP monitoring process
- Provision of final study report

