9.2. Populations for Analyses

The main population for analyses will consist of all consented participants who have the requested baseline data and at least one post-baseline assessment data.

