9.3.3. Secondary Analyses

Patients' renal functional change during TDF treatment period will be explored.

- The proportion of patients whose eGFR (MDRD equation) decline >20% from baseline at weeks of 48, 96 and up to week 144 will be summarized for the overall study analysis population and sub-group populations.
- Mean and 95% confidence intervals for the change from baseline in eGFR values will be calculated for the overall analysis population, as well as for the subpopulations of interests. A mixed effect model will be fitted to explore the impacts on the mean change from baseline in eGFR of fixed effects of age, gender, treatment-naïve or experienced, ADV or non-ADV, type of baseline comorbidities (Cirrhosis, Hypertension, diabetes mellitus (DM), non-overlapping), baseline eGFR values, baseline HBV-DNA counts, baseline HBeAg status, and other factors as appropriate, and random effects of subject ID.
- The percentage of change from baseline in eGFR will be estimated for the overall analysis population and by sub-populations at weeks 48, 96, and 144. Figures of mean eGFR values overall and the sub-populations of interests will be generated.
- The proportion of patients with confirmed a serum phosphate Grade 3 or 4 abnormality (<2.0 mg/dL) at weeks of 48, 98 and 144 will be summarized for the overall study analysis population and sub-group populations.
- The percentage of change from baseline in serum phosphate will be estimated for the overall analysis population and by sub-populations at weeks 48, 96, and 144. Figures of mean serum phosphate values overall and the sub-populations of interests will be generated.
- Mean and 95% confidence intervals for the change from baseline in serum phosphate values will be calculated for the overall analysis population, as well as for the sub-populations of interests. A mixed effect model will be fitted to explore the impacts on the mean change from baseline in serum phosphate of fixed effects of age, gender, treatment-naïve or experienced, ADV or non-ADV, type of baseline co-morbidities (Cirrhosis, Hypertension, DM, non-overlapping), baseline eGFR values, baseline HBV-DNA counts, baseline HBeAg status, baseline phosphorus and other factors as appropriate, and random effects of subject ID.

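### The Grade 3 or 4 phosphate proportion has no baseline condition, so it mixes low phosphate present before TDF with new on-treatment cases

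*Protocol*

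**What the plan says.** Section 9.3.3 of the protocol names the endpoint as "The proportion of patients with confirmed a serum phosphate Grade 3 or 4 abnormality (<2.0 mg/dL) at weeks of 48, 98 and 144". Table 2 in Section 4 has the same definition, "Proportion of patients with confirmed serum phosphate Grade 3 or 4 abnormality (<2.0 mg/dL", and the synopsis repeats it. Section 9.3.3 also fixes whom it is reported in: it "will be summarized for the overall study analysis population and sub-group populations". Section 9.2 defines the main population without mentioning phosphate levels: "The main population for analyses will consist of all consented participants who have the requested baseline data and at least one post-baseline assessment data".

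The objective in Table 2 begins "To assess the renal function change among overall and sub-group CHB patients during TDF", and Section 7.4 adds "Our special interest is the renal and bone toxicity related to TDF". The companion eGFR proportion is defined against baseline: "The proportion of patients whose eGFR (MDRD equation) decline >20% from baseline at weeks of 48, 96 and up to week 144". The other eGFR and phosphate estimates in Section 9.3.3 are changes or percentage changes from baseline, apart from plots of mean values.

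Section 6.2 excludes nobody for low phosphate or kidney disease. Sections 4 and 9.3.2 name kidney disease and earlier treatment with other NUCs as sub-group factors.

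**The concern.** The objective asks what happens to renal function while patients take TDF. A patient who starts TDF below 2.0 mg/dL and stays there has not changed, yet meets the definition at every time point. The requirement that the abnormality be confirmed does not screen such a patient out, since a persistent low value will also be confirmed.

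Patients like this can be enrolled, because renal disease and earlier NUC treatment are expected in the cohort and are not grounds for exclusion. Section 3.1 says that NUC nephrotoxicity, first seen with adefovir in HIV-infected patients, "primarily results in proximal tubular toxicity rather than glomerular toxicity", and it links tubule damage to lower serum phosphate.

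Two uses of the number are at stake. Section 9.3 plans tests across sub-groups, so a contrast by earlier NUC treatment or renal disease could reflect who was already low. Section 12 suggests a historical comparison with trial data to offset the lack of a control group. Section 3.2 ties the 48-week registration finding on renal toxicity to patients whose renal function was preserved at baseline, so a proportion that includes baseline-low patients may not be like for like.

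**Working it through.** **The plan's own figures.** The protocol gives no figure for this endpoint. The 1,300 used below comes from Section 9.1.2: 2000 × (1 − 0.35) = 1300. The precision stated there reproduces: 1.96 × √(0.80 × 0.20 / 1300) = 0.0217, stated as 2.2%. So does the chance of seeing at least one event with a true rate of 0.1%: 1 − 0.999^1300 = 72.8%, stated as about 73%.

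**Inputs for the illustration.**
- b, the share of patients below 2.0 mg/dL before TDF: not in the protocol; assumed 0 to 2%.
- k, the share of those still low at the visit: not in the protocol; assumed 50%, with 100% as a check.
- i, the rate of new low phosphate at the visit among patients not low at baseline: assumed 1 to 2%. The nearest anchors are in Section 3.2: individual renal events at no more than 2.2% over 8 years, and nearly 1% renal adverse events in the Chinese Phase III study. Both describe events over follow-up, not prevalence at one visit, so they only indicate scale.

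**Formulas.**
- Proportion as worded = b·k + (1 − b)·i
- Share pre-existing = b·k / [b·k + (1 − b)·i]
- Proportion restricted to baseline ≥2.0 mg/dL = i

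**Results with k = 50%.**

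| b | i | As worded | Share pre-existing | Restricted |
|---|---|---|---|---|
| 0% | 1% | 0 + 1.00 = 1.00% | 0% | 1% |
| 0% | 2% | 0 + 2.00 = 2.00% | 0% | 2% |
| 0.5% | 1% | 0.25 + 0.995 = 1.245% | 20% | 1% |
| 0.5% | 2% | 0.25 + 1.99 = 2.24% | 11% | 2% |
| 1% | 1% | 0.50 + 0.99 = 1.49% | 34% | 1% |
| 1% | 2% | 0.50 + 1.98 = 2.48% | 20% | 2% |
| 2% | 1% | 1.00 + 0.98 = 1.98% | 51% | 1% |
| 2% | 2% | 1.00 + 1.96 = 2.96% | 34% | 2% |

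If every baseline-low patient stayed low (k = 100%), b = 2% and i = 1% would give 2.00 + 0.98 = 2.98%, of which 67% is pre-existing.

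**In patients.** Take 1300 with a value, b = 1%, k = 50% and i = 1%. The endpoint as worded counts 6.5 + 12.9 = 19.4 of 1300. The restricted version counts 12.9 of 1287, which is 1.00%.

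**Effect on a sub-group contrast.** Suppose two sub-groups share a new-case rate of 1%, one with b = 0 and the other with b = 2% and k = 50%. The endpoint as worded shows 1.00% against 1.98%. The apparent doubling comes entirely from baseline.

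**The case against.** The strongest reply is that the protocol is merely silent. Treatment-emergent rules and shift tables usually belong in the analysis plan, and Section 9.3 defers detail to a RAP that is not shown. This has some force, and the RAP may already contain such a table. But the protocol does more than leave a gap: it states the threshold, the time points and the population, and a RAP that followed it would report the mixed proportion. Where the protocol wants an at-risk denominator it writes one, as for HBeAg loss in HBeAg-positive patients (Section 9.3.2).

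A second reply is that an absolute threshold is reasonable. Section 3.2 reports the registration trials' phosphate event as an absolute level, and Section 12 looks to historical comparison. That supports keeping the 2.0 mg/dL cut-off. It does not settle who belongs in the denominator, and the protocol does not say how those trials handled patients already low at baseline.

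Three stronger readings are tempting and are not supported:
- A reader might infer that each low value is counted as TDF toxicity. The protocol does not say so. The study is descriptive with no hypotheses (Section 9.1.1), and the lack of a comparison group is acknowledged (Section 12).
- A reader might infer that an adefovir versus non-adefovir comparison of this proportion will display old damage. Section 9.3.3 uses that factor only in the models for mean change, and the phosphate model also carries baseline phosphorus. For the proportion, the named sub-group factor is earlier treatment with other NUCs. The adefovir remark in Section 3.1 concerns HIV-infected patients, whom Section 6.2 excludes.
- A reader might infer that recovery after leaving adefovir would be invisible. Average recovery would show in the planned mean and percentage changes. What these cannot do is tell which patients below 2.0 mg/dL at a visit were already below it at the start.

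**Conclusion.** The point holds as a matter of definition. As written, the endpoint is a point prevalence of confirmed low phosphate, not a measure of new low phosphate during TDF, and so it does not match its objective. Sub-group contrasts and historical comparisons of this proportion inherit the mixture.

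The size cannot be determined from the protocol. The range of 0% to about 51% pre-existing rests wholly on assumed prevalence, persistence and new-case rates. It is nil if nobody is low at baseline, and higher if more than half stay low. It should not be read as an estimate of bias.

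This is a worthwhile correction to a secondary, descriptive endpoint. It leaves the primary effectiveness results and the baseline-referenced renal analyses untouched. It still merits the change, because Section 3.2 names physicians' concern about renal safety as one the study is meant to address.

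**What to change.** Reword the endpoint in Section 9.3.3, Table 2 and the synopsis, and carry it into the RAP:
- **Main estimate:** the proportion with confirmed phosphate below 2.0 mg/dL at the time point, among patients with baseline phosphate of at least 2.0 mg/dL and a value at that time point.
- **Shift table:** baseline (below 2.0, or 2.0 and above) against each visit (below 2.0, 2.0 and above, missing), overall and by earlier NUC and adefovir history. Baseline-low patients then appear separately, and both persistence and recovery can be read off.
- **Baseline:** state that it means the value at TDF initiation. For patients already on TDF at entry, an entry value could class a case that arose on TDF as pre-existing. Section 6.1 requires an initiation value for these patients, within 4 weeks either side, and caps them below 10% of the cohort.

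The present overall proportion can stay as a supplementary line if it is labelled as prevalence. The cost is wording, a slightly smaller denominator (1287 in place of 1300 at an assumed 1% baseline prevalence) and one extra table. Baseline phosphate is already collected (Table 1, Sections 6.1 and 7.2), so no new test or visit is needed. The same edit should reconcile week 98 in this bullet with week 96 elsewhere in Section 9.3.3, which is a separate discrepancy.

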9.3.4. Exploratory Analyses

9.3.4.1. Bone safety

Patients' BMD change from baseline during TDF treatment period will be explored.

• Percentage of BMD change at weeks of 48, 96, and 144 will be summarized using appropriate descriptive statistics for the overall analysis population and by subgroup populations.

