2. SCHEDULE OF ACTIVITIES (SOA)

The exact timing of each assessment is listed in the Schedule of Activities Table 1

Table 1 Schedule of Activities

	Patients who have started TDF prior to entry of study Patients who newly initiate TDF								
Procedure			newly initiate	Follow-up data collection period (3 years) ⁶					
	Initiation of TDF treatment	Entry of study	Entry of study	6 months	12 months	18 months	24 months	30 months	36 months
Informed consent		Χ	Χ						
Inclusion and exclusion criteria		Χ	X						
Baseline assessments ¹									
Sociodemographic		Χ	X						
Health behaviour		Χ	X						
Physical examination		Χ	X						
Medical history	X	Χ	Χ						
Regular assessments ^{2,3}									
HBV serology	X	Х	Х	Χ	Х	Х	Х	Χ	Х
HBV DNA *	X	Х	Х	Χ	Х	Х	Х	Χ	Х
ALT and/or AST	X	Χ	Х	Χ	Х	Х	Х	Χ	Х
Serum creatinine and eGFR [MDRD equation] *	Х	Χ	Х	Х	Х	Х	Х	Х	Х
Serum phosphate*	Х	Х	Х	Χ	Х	Х	Х	Х	Х
TDF treatment status or update	Х	Х	Х	Х	Х	Х	Х	Х	Х
Comorbidity and concomitant medication review	Х	Х	Х	Х	Х	Х	Х	Х	Х

	Ва	Baseline data collection⁵			F II				
Procedure	Patients who have started TDF prior to entry of study		Patients who newly initiate TDF		Follow-up data collection period (3 yea			s years)°	
	Initiation of TDF treatment	Entry of study	Entry of study	6 months	12 months	18 months	24 months	30 months	36 months
Patients adherence to TDF treatment		Χ		Х	Х	Х	Х	Х	Х
Other assessments ^{2,3}									
AFP		Χ	X	Χ	Х	Х	Х	Χ	Χ
Hepatic ultrasound		Х	Х	Х	Х	Х	Х	Х	Х
Genotype		Х	Х	Χ	Х	Х	Х	Х	Х
Bone mineral density (BMD)		Х	Х	Χ	Х	Х	Х	Х	Χ
Liver biopsy		Х	Х	Χ	Χ	Χ	Χ	Χ	Χ
Transient elastography		Х	Х	Χ	Х	Х	Х	Х	Х
computed tomography (CT) /magnetic resonance imaging (MRI)		Х	Х	Х	Х	Х	Х	Х	Х
Spontaneous AE/SAEs and pregna	ncy exposure d	lata collection4	•	•	•	•	•	•	•
Spontaneous AE/SAEs reporting		Х	Х	Χ	Χ	Х	Х	Χ	Χ
Pregnancy exposure reporting		Х	Х	Χ	Χ	Х	Х	Х	Χ

2017N314002_00 **CONFIDENTIAL** 207667

Abbreviations and notes:

AEs = Adverse events; CT= computed tomography; DNA = Deoxyribonucleic acid; eGFR = estimated Glomerular filtration rate; HBV = Hepatitis B virus; HBeAg = Hepatitis B envelope antigen; HCC = Hepatocellular carcinoma; MDRD = Modification of Diet in Renal Disease; MRI = Magnetic resonance imaging; SAEs = Serious adverse events AFP = Alpha feto protein * the essential lab test performed in central lab at or after entry of study

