- 1. Sociodemographic: a brief baseline survey will be administered to collect a minimal amount of information. Additional study relevant information (only for enrolled patients) will be collected to enable study analyses.
- 2. Laboratory assessments and other clinical assessments: patients will only be monitored according to their physicians' standard practice without additional study-specified interventions and evaluations. Only available assessments will be collected from routine testing/evaluations using electronic approaches.
- 3. Assessments may not be conducted at the exact scheduled time intervals as there will be no intervention for patients' clinical care. Only available assessments will be collected from routine testing/evaluations. The schedule is to remind physicians to collect data regularly.
- 4. Adverse event and pregnancy exposure reporting: only spontaneous AEs/SAEs and pregnancy exposure related to any GSK products will be reported and summarized.
- 5. The baseline assessment filling with grey colure is mandatory and requested for baseline data collection.
- 6. Follow-up data collection period (e.g. months 6, 12, 18, 24, 30, 36) for patients who have started TDF before the entry of study will be anchored to their actual TDF initiation dates.

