The effectiveness and renal safety results of TDF varies between registered clinical trials [complete virological response (CVR) over 95%] and real-world research (CVR approximately 71 to 92%) [Pol, 2012, Idilman, 2015, Kim, 2015], partly due to the difference between clinical trial patient population and real world study population. Phase III clinical trials are conducted under well-controlled conditions among pre-selected patients with strict in/exclusion criteria, generally eliminating older patients and those with co-infections or comorbidities (such as cirrhosis). Compared with most patients seen in real world practice, those participating in clinical trials are typically younger and healthier with less comorbidity and better treatment adherence. Understanding how antivirals perform in real world general patient population is more important to guide routine clinical practice. The results from high-quality real-world cohorts will continue to provide clinical guidance for physicians by providing safety and effectiveness evidence across diverse treatment settings and in a broader array of patients and enable more patients to benefit from the available treatment options.

Lampertico et al. [Lampertico, 2016] reviewed recent real-world evidence on the safety of TDF treatment among HBV-monoinfected patients. Overall, TDF can lead to minor reduction in eGFR and BMD, which was mainly observed during early stage of treatment and remained stable in long-term follow up in most patients. Although TDF was well tolerated with no clinically significant renal toxicity, evidence from cohort studies seems to be conflicting. Reductions in GFR/Creatinine among HBV patients treated with TDF were reported, the clinical significance of these changes needs more discussion and the degree of association between TDF and changes in renal function indicators varies across studies. The inconsistency might result from small sample size, different baseline population with different renal function, varying measures of renal function. Few studies observed BMD during TDF treatment among CHB patients. Gill et al. carried out a single-centre cohort study in the UK, specifically to assess the impact of TDF on BMD in 170 HBV-monoinfected patients. There was no difference in T-score between treatment groups for lumbar or femoral neck measures, but TDF was associated with a lower hip T-score compared with no TDF (P = 0.02) [Gill, 2015].

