All the lab test and procedures in the SoA will be performed based on the judgement of investigators/treating physicians and patients' willingness as in real-world practice. To achieve consistent evaluation of the effectiveness and safety of TDF treatment, the minimal essential lab test requested by CHB management guideline, including HBV DNA, eGFR and serum phosphate, will be performed in central lab during patients'

routine clinical visits. Other lab tests and procedures will be performed in local hospitals where patients seek care. Results will be collected by the innovative electronic approach.

CONFIDENTIAL

Supplementary central lab operation information would be provided in the accompanying study procedure manual (SPM). The SPM will provide the site personnel with administrative and detailed information on how to minimize the impact of the introduction of central lab to routine practice.

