7.2. Baseline Data Collection

Baseline information collected (assessment values and date of assessment) includes:

- Socio-demographic information, e.g. age, sex, economic status, medical insurance coverage
- Health behaviour information, e.g. smoking status, alcohol consumption, health care seeking behaviour
- Physical examinations, e.g. weight, height
- Medical information, e.g. medical history, anti-Hep B diagnosis and treatment history, NUC drug resistance history, co-morbidity, concomitant treatment, decompensated cirrhosis/liver disease and related complications
- TDF treatment details, e.g. TDF dose, brand name, start date
- Initial tests when initiating TDF therapy, including
 - HBV serology
 - o HBV DNA
 - o Serum creatinine and eGFR [MDRD equation]
 - Serum phosphate
 - o Alanine transaminase (ALT) and aspartate transaminase (AST)
- Other tests and procedures collected if available
 - o AFP

- Hepatic ultrasound
- o Genotype
- o Bone mineral density
- o Liver biopsy
- o Transient elastography (fibrotouch or fibroscan)
- Hepatic ultrasound/ computed tomography (CT) /magnetic resonance imaging (MRI)
- Spontaneous AEs if available

To evaluate renal function, the estimated glomerular filtration rate (eGFR) will be calculated using the modification of Diet in Renal Disease (MDRD) equation:

Where the unit of creatinine is ml/min/1.73m². Baseline data will be collected using a specifically designed survey. For patients who initiate TDF treatment at the entry of the study, baseline information can be completed from investigator interviewing the patient.

For patients who have already been on TDF treatment at the study entry, their previous data related to initiation of TDF treatment and follow-up will be collected from (electronic) medical records as needed if available.

Three essential lab tests, HBV DNA, serum creatinine, and serum phosphate, will be performed in a central lab. Patients' other data will be collected using electronic approaches, mainly from lab test reports or medical records at baseline and follow-ups.

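### For already-treated patients the scheduled BMD baseline falls after TDF start while their weeks run from TDF start, and no skeletal site is required with any scan (minor, exploratory endpoint)

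*Protocol*

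**What the plan says.** Section 9.3.4.1 plans the bone summary as follows: "Percentage of BMD change at weeks of 48, 96, and 144 will be summarized using appropriate descriptive statistics for the overall analysis population", and also by subgroup. Section 9.2 defines the main population as "all consented participants who have the requested baseline data and at least one post-baseline assessment data", with no specific requirement for a BMD value.

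BMD is optional and local. Section 7.2 lists it under "Other tests and procedures collected if available". Note 2 to the Schedule of Activities (section 2) says "Only available assessments will be collected from routine testing/evaluations using electronic approaches". Section 7 sends HBV DNA, eGFR and serum phosphate to a central laboratory and adds: "Other lab tests and procedures will be performed in local hospitals where patients seek care". No section names a skeletal site, a scan method or a device rule for BMD.

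In the Schedule of Activities the BMD row is empty in the column for TDF initiation, which applies to patients who started TDF before entry. It is marked at study entry and at months 6 to 36. Note 6 says that the follow-up period "for patients who have started TDF before the entry of study will be anchored to their actual TDF initiation dates".

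Section 3.2 reports bone findings by site. One cited cohort is summarised thus: "There was no difference in T-score between treatment groups for lumbar or femoral neck measures, but TDF was associated with a lower hip T-score". The same section says that hip and spine T scores in the global registration study were stable between years 4 and 8.

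**The concern.** A percentage change from baseline needs a baseline that belongs to the same clock as the follow-up weeks, and two measurements of the same thing. The protocol leaves both open for BMD.

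First, for already-treated patients the first scheduled BMD is at study entry, after TDF has begun, while weeks 48, 96 and 144 run from TDF start. If bone is lost after TDF start, some of the loss precedes their baseline and drops out of the reported change. Section 3.2 says that reductions in BMD were mainly seen early in treatment, which is the part such a baseline would miss.

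Second, if the site is not recorded with each scan, a patient's baseline and follow-up may come from different sites, and the summary may average sites that behave differently. BMD decline is also an outcome of the exploratory risk-factor objective in section 4, so the problem would carry over to that analysis.

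**Working it through.** **The plan's own figure.** There is none for BMD. The only stated precision, in section 9.1.2, is for CVR: 1.96 × √(0.80 × 0.20 / 1300) = 0.0217, which agrees with the stated 0.022. It says nothing about BMD, because the protocol does not say how many patients will have paired scans.

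**Step 1: baseline and clock side by side.** At TDF initiation the schedule marks HBV serology, HBV DNA, ALT/AST, creatinine with eGFR, and phosphate, but not BMD. The essential TDF-start records in inclusion criterion 4 (section 6.1) also omit BMD. Section 7.2 allows earlier data to be taken from medical records as needed and if available, so a TDF-start scan is possible but not required. Followed as written, the scheduled BMD baseline is at entry and the clock starts at TDF initiation.

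**Step 2: one patient.** Fraction of exposure captured = (week − entry week) / week. Assume entry at week 48 of TDF.
- At week 96: (96 − 48) / 96 = 0.50.
- At week 144: (144 − 48) / 144 = 0.67.

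These are also the fractions of the change captured if loss is linear. If loss is early, less is captured.

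**Step 3: effect on the pooled mean.** Pooled mean / true mean = 1 − q(1 − c), where q is the share of BMD pairs from already-treated patients and c is the fraction of change they capture. Section 6.1 keeps these patients below 10% of the cohort, that is, fewer than 0.10 × 2000 = 200. Their share of BMD pairs is not given and could differ.

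| q (assumed) | c = 0 | c = 0.5 |
|---|---|---|
| 10% | 0.90 | 0.95 |
| 20% | 0.80 | 0.90 |
| 30% | 0.70 | 0.85 |

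**Step 4: mixing sites.** Pooled change = w × (hip change) + (1 − w) × (change elsewhere), where w is the share of hip scans. All inputs are assumptions.
- Hip −2%, elsewhere 0%: w = 30% gives −0.6%; w = 70% gives −1.4%.
- Hip −2%, elsewhere −0.5%: w = 25% gives 0.25 × (−2) + 0.75 × (−0.5) = −0.875%; w = 75% gives −1.625%.

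In each case the hip change is diluted but still present.

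**The case against.** The strongest reply is that silence is being read as a plan. Section 9.3.4.1 never says that sites will be pooled, and sections 9.3 and 9.3.5 leave analysis detail to a Reporting and Analysis Plan that is not at hand. Site-specific tables and same-site pairing would normally sit there, and section 3.2 shows that the authors know BMD is reported by site. This stands: the protocol permits mixing and does not prescribe it. What the reply does not remove is that an analysis plan can only use a site that was captured at upload. The protocol does not list the uploaded fields, so loss of this information is a risk and has not been shown.

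The already-treated group is small, earlier scans may be retrieved, and section 12 already admits inconsistent baseline information when new and on-treatment patients are mixed. This also stands and limits the size. However, the remedy that section 12 offers, restricting inclusion of already-treated patients, does not reach BMD, because criterion 4 does not ask for it.

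The cited hip finding is a between-group T-score comparison in one centre with 170 patients. It is not a within-patient percentage change, and section 3.2 also cites stable T scores and a three-year analysis with no significant BMD change. It therefore supports keeping sites apart but does not establish a hip effect of any size.

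A reader might also infer that the words about the overall analysis population mislabel a scanned minority. They do not: the phrase contrasts with the subgroups, as it does for eGFR in section 9.3.3. Sections 2 and 7 say that only available results are collected, and section 9.3.5 says that missing values will in general not be imputed.

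**Conclusion.** The point holds as a minor one. The mismatch between the scheduled BMD baseline and the TDF-start clock is in the protocol's own schedule. It affects fewer than 10% of patients and matters only where no earlier scan is retrieved and BMD falls after TDF start. If these patients form 10% of pairs and capture 0 to 50% of the change, the pooled mean is understated by 5% to 10% of its value. If they form 30% of pairs, it is understated by 15% to 30%. The possible mixing of sites follows from a missing requirement, and its size cannot be derived from the document.

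Two stronger readings are tempting and unsupported. One is that the plan cannot show a hip effect: under the assumptions above it is diluted, not removed. The other is that differences between devices exceed the true change: the protocol gives neither a device error nor an expected BMD effect. Offsets in both directions would add noise rather than a consistent bias. Nor does the protocol give the number of patients who will be scanned, so how few or how selected they are is unknown. The study tests no hypotheses and the BMD objective is exploratory, so nothing here touches the primary or secondary results.

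**What to change.** - Record the skeletal site, and the device or hospital, with each uploaded BMD result.
- In section 9.3.4.1, summarise percentage change separately for hip, femoral neck and lumbar spine, using within-patient pairs from the same site. Add same-device pairs as a sensitivity analysis.
- Include already-treated patients in change from baseline only if they have a scan at or before TDF initiation. Otherwise report them separately.
- Give the number of paired scans at weeks 48, 96 and 144.

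The cost is two data fields and some wording. No extra scan is asked for and patient care does not change. The downside is fewer usable BMD pairs in each summary, which is why the same-device restriction belongs in the sensitivity analysis and not in the main one.
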